9.2. Population PK Analyses

GSK2982772 plasma concentrations from this study may be included in a cross-study population pharmacokinetic (Pop PK) analysis. If deemed appropriate to conduct a Pop PK analysis, a NONMEM datafile will be generated. The details for the dataset specifications are provided in [Appendix 12](#).

9.3. Pharmacokinetic/Pharmacodynamic Analyses

The relationship between GSK2982772 predicted trough concentration and the following variables will be explored graphically:

- Target engagement from the corresponding blood/biopsy tissue sample;
- Change from baseline in continuous efficacy endpoints (Total Mayo Score, Partial Mayo Score, 3-domain Mayo Score, UCEIS Total Score, Modified Riley Scale Score, Geboes Index Total Score, RHI Score, CRP and FCP).

Box plot of GSK2982772 concentrations in participants not achieving a Mayo Endoscopy Remission and participants achieving a Mayo Endoscopy Remission.

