No endpoint and derivations for the Roberts Histology Index (RHI) was explicitly mentioned in the protocol. The protocol endpoints section states: Change from baseline on histologic severity including but not limited to MRS and Geboes. Roberts will also provide GSK with the RHI alongside the MRS and Geboes.	Relevant definitions for the RHI and required summaries were added to the RAP	To enable analysis of the RHI data.
GSK2982772 plasma concentrations will be summarised descriptively by day and nominal sampling time (Pre-dose on Day 43 and at 1, 2, 4, and 6 hours post dose on Days 1 and 43 and trough on Day 85 or Early Withdrawal).	The predicted trough concentration at 7am on Day 43 will be calculated using the observed pre-dose concentration at the time of the PK sample (see Section 9.1.1.1 for calculations) The predicted Day 43 trough concentration will be used in PK/PD assessments instead of the observed Day 43 Pre-Dose concentration	Since the half-life of GSK2982772 is short (2-3h), the duration of time between the Day 43 clinic visit and the usual dosing time (assumed to be 7am for all subjects) may result in the reported "pre-dose" concentration being lower than the true "trough concentration"

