9. PHARMACOKINETIC ANALYSES

9.1. Pharmacokinetic Analyses

9.1.1. Endpoint / Variables

9.1.1.1. Drug Concentration Measures

PK plasma and biopsy tissue Concentration data for GSK2982772 will be summarised and listed, no statistical analysis will be conducted. Summary statistics of GSK2982772 concentration by Day (1, 43, and 85) and nominal blood sampling time will be determined. PK blood samples are taken pre-dose on Day 43 and post-dose on Days 1 and Day 43 at the following time points: 1, 2, 4, and 6 hours and trough on Day 85 or Early Withdrawal.

PK data will be summarised for Parts A and B by randomised treatment.

Refer to [Appendix 5: Data Display Standards & Handling Conventions \(Section 12.5.3 Reporting Standards for Pharmacokinetic\)](#).

Table 7 Overview of Planned Pharmacokinetic Analyses

Endpoints	Untransformed				Log-transformed			
	Summary		Individual		Summary		Individual	
	T	F	F	L	T	F	F	L
Pharmacokinetic								
Plasma Drug concentration	Y	Y ^[1] 2	Y ^[1]	Y				
Biopsy Tissue Drug concentration	Y	Y ^[1] 2	Y ^[1]	Y				

NOTES:

- T = Table, F = Figure, L = Listings, Y = Display generated.
 - Summary = represents TF related to any summaries (i.e. descriptive statistics) of the observed raw data.
 - Individual = represents FL related to any displays of individual participant observed raw data.
- 1: Linear and Semi-Log plots will be created on the same display.
2: Separate Mean (\pm SE) and Median plots will be generated.

Since the half-life of GSK2982772 is short (2-3h), the duration of time between the Day 43 clinic visit and the usual dosing time may result in the reported “pre-dose” concentration being lower than the true “pre-dose” or trough concentration (e.g. if the usual dose time was 7am and the clinic visit was 10am the “pre-dose” sample collected at 10 am would be approximately $\frac{1}{2}$ that of the true “trough” concentration assuming a 3 hour half-life). Therefore, the predicted “trough” concentration will be calculated using the following equation-

$$C_{trough} = C_{predose} + (e^{-(k_e \times t)})$$

where

- C_{trough} = predicted trough concentration prior to usual dosing time
- $C_{predose}$ = observed “pre-dose” concentration collected at the clinic
- t = time in hours between pre-dose blood sample collection and time of dosing (assumed to be 7am)
- k_e = elimination rate constant ($0.693 / t_{1/2}$), ($t_{1/2}$ assumed to be 2.5h)

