12.10.10. Pharmacokinetic Figures

Pharmacokinetic: Figures					
No.	Population	IDSL / Example Shell	Title	Programming Notes	Deliverable [Priority]
Individual PK Concentration					
4.1.					
Mean/Median Concentration					
4.2.	PK	PKCF2	Mean (\pm SE) Plot: GSK2982772 Concentrations versus Time (Linear) on Day 1 and Day 43 (60 mg TID only)		IA SAC [1] SAC [1]
4.3.					
Trough Concentration					
4.4.	PK		GSK2982772 Observed pre-dose Concentration Data vs Day (60 TID only)	Separate pages for plasma Spaghetti Plot of individual trough concentrations vs day.	IA SAC [1] SAC [1]
4.5.	PK		GSK2982772 Observed Pre-Dose Concentration Data vs Day	Plot of individual trough concentrations vs day overlaid with box and whisker plot.	IA SAC [1] SAC [1]
4.6.	PK	PD_F1	Scatter Plot GSK2982772 Observed Pre-Dose Plasma Concentration Versus Biopsy Pre-Dose Tissue Concentration	X axis – Plasma Y axis – Biopsy	IA SAC [1] SAC [1]
PK/PD					
4.7.	PK	PD_F1	Scatter Plot of Individual GSK2982772 Pre-Dose Concentrations Versus Individual Pre-Dose % Target Engagement	Separate pages sample type (Plasma/Biopsy) X axis – PK concentration, Y axis – TE	IA SAC [1] SAC [1]

Pharmacokinetic: Figures					
No.	Population	IDSL / Example Shell	Title	Programming Notes	Deliverable [Priority]
4.8.	PK	PD_F1	Box Plots of GSK2982772 Day 43 Predicted Trough Concentration for participants not achieving Mayo Endoscopy Remission and for participants achieving Mayo Endoscopy Remission	Separate pages sample type (predicted trough /Biopsy) X axis – Non Mayo Endoscopy Remission / Mayo Endoscopy Remission Y axis – PK Conc	IA SAC [1] SAC [1]
4.9.	PK	PD_F1	Scatter Plot of Individual GSK2982772 Predicted Trough Concentration Versus Change from Baseline in Total Mayo Score	Separate pages sample type (Blood/Biopsy) X axis – PK concentration, Y axis – Efficacy Parameter	IA SAC [1] SAC [1]
4.10.	PK	PD_F1	Scatter Plot of Individual GSK2982772 Predicted Trough Concentration Versus Change from Baseline in Partial Mayo Score	Separate pages sample type (Blood/Biopsy) X axis – PK concentration, Y axis – Efficacy Parameter	IA SAC [1] SAC [1]
4.11.	PK	PD_F1	Scatter Plot of Individual GSK2982772 Predicted Trough Concentration Versus Change from Baseline in 3-domain Mayo Score	Separate pages sample type (Blood/Biopsy) X axis – PK concentration, Y axis – Efficacy Parameter	IA SAC [1] SAC [1]

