12.10.11. Pharmacodynamic and/or Biomarker Tables

Pharmacodynamic and Biomarker: Tables					
No.	Population	IDSL / Example Shell	Title	Programming Notes	Deliverable [Priority]
Exploratory Biomarkers					
6.1.	Safety	PD_T1	Summary Statistics for Actual and Percentage Change from Baseline in Biopsy Tissue Inflammatory Biomarkers (Parts A and B)	One page for each cell type/measure by visit/time and treatment	SAC [1]
6.2.	Safety	PD_T2	Adjusted Mean (95% CI) of Percentage Change from Baseline in Biopsy Tissue Inflammatory Biomarkers (Parts A and B)	One page for each cell type/measure by visit/time and treatment/dosing regimen	SAC [1]
Pathway and Target Engagement					
6.3.	Safety	EFF_T1	Summary Statistics for Observed TEAR1 % Target Engagement (Parts A and B)	Separate summaries for sample type (Blood/Biopsy) % Target Engagement by visit/time	SAC [1]
6.4.			Summary Statistics for Predicted TEAR1 % Target Engagement based on predicted GSK2982772 trough concentrations (Parts A and B)		
6.5.	Safety	PD_T3	Adjusted Mean (95% CI) of TEAR1 % Target Engagement in Blood (Parts A and B) by Randomised Treatment		SAC [1]
6.6.	Safety	PD_T3	Adjusted Mean (95% CI) of TEAR1 % Target Engagement in Biopsy Tissue (Parts A and B) by Randomised Treatment		SAC [1]
6.7.	Safety	EFF_T1	Summary Statistics of Pathway Engagement (Parts A and B) by Randomised Treatment	Separate summaries for sample type (Blood/Biopsy)	SAC [1]
6.8.	Safety	PD_T3	Adjusted Mean (95% CI) of Pathway Engagement in Blood (Parts A and B) by Randomised Treatment		SAC [1]
6.9.	Safety	PD_T3	Adjusted Mean (95% CI) of Pathway Engagement in Biopsy Tissue (Parts A and B) by Randomised Treatment		SAC [1]

Pharmacodynamic and Biomarker: Tables					
No.	Population	IDSL / Example Shell	Title	Programming Notes	Deliverable [Priority]
mRNA Expression					
6.10.	Safety	PD_T4	Summary of mRNA Expression of Inflammatory Gene Transcripts (Parts A and B) by Randomised Treatment	Separate summaries for sample type (Blood/Biopsy) qPCR – micarray dataset	SAC2 [1]
6.11.	Safety	PD_T5	Frequency Table Summarising the Number of Probe Sets with Various Fold Change (Parts A and B) by Randomised Treatment	Separate summaries for sample type (Blood/Biopsy). Use cut-offs 1.5 and -1.5 initially. Change to -1.25 and 1.5 if no one achieves the initial cut-offs	SAC2 [1]

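### For Day 43 plasma, section 9.3 plots engagement from the clinic sample against a concentration predicted for 7am, so the pair is mismatched in time and the text conflicts with Figure 4.7

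*SAP*

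**What the plan says.** Three parts of the SAP bear on which concentration goes with target engagement.

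- **Analysis text.** Section 9.3 opens: "The relationship between GSK2982772 predicted trough concentration and the following variables will be explored graphically". The first variable under it is "Target engagement from the corresponding blood/biopsy tissue sample"; the continuous efficacy endpoints follow.
- **Changes table.** Table 1 in section 2.1 states: "The predicted Day 43 trough concentration will be used in PK/PD assessments instead of the observed Day 43 Pre-Dose concentration". It makes no exception for engagement.
- **Display list.** In section 12.10.10, Figure 4.7 is titled "Scatter Plot of Individual GSK2982772 Pre-Dose Concentrations Versus Individual Pre-Dose % Target Engagement". The title of Figure 4.18 makes the same pairing for TEAR1 engagement, although its axis note calls the concentration a trough. Figures 4.8 to 4.17, which cover endoscopy remission and the efficacy scores and markers, are titled with the predicted trough.

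Section 9.1.1.1 defines the predicted trough as the Day 43 pre-dose value carried back to the usual dosing time. That time is taken as 7am for everyone, and the half-life is "assumed to be 2.5h". In the schedule of activities (section 12.2.1), the Day 43 blood samples for engagement and for PK are both marked pre-dose, and the morning dose must not be taken at home that day.

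**The concern.** Engagement in the Day 43 blood sample describes the participant at the moment of the draw. The predicted trough describes the same participant at 7am. The SAP introduces the prediction because the concentration may have fallen appreciably between those two times. Moving only the concentration back to 7am breaks the same-sample pairing that section 9.3 itself asks for.

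A programmer also cannot follow both instructions. Section 9.3 and Table 1 call for the predicted value, while Figure 4.7 calls for the pre-dose value. No listed figure is titled predicted trough against engagement, so the first item in section 9.3 has no matching display.

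At stake is how the exposure-engagement plot is read. If it were drawn as section 9.3 says, a given level of engagement would sit at a higher concentration than the one in the sample. The size of the shift would differ between participants with their clinic times.

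**Working it through.** **Inputs**

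- Half-life used for the prediction: 2.5 h; range given: 2 to 3 h (section 9.1.1.1).
- Elimination rate constant: ke = 0.693 / half-life (section 9.1.1.1), so ke = 0.693 / 2.5 = 0.277 per hour.
- Reference time: 7am (sections 2.1 and 9.1.1.1).
- Delay from 7am to the sample: not given. The SAP's example uses 3 h (7am to 10am); 1 h and 2 h are assumed here for comparison.

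**Step 1: reproduce the SAP's example.** With a 3 h half-life and a 3 h delay, C(10am) / C(7am) = exp(−(0.693/3) × 3) = exp(−0.693) = 0.50. This matches the SAP's statement that the late sample is about half the true trough. Undoing that decay means multiplying by exp(ke × t).

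**Step 2: plotted concentration over concentration in the sample, exp(ke × t).**

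| Delay | Half-life 2.5 h |
|---|---|
| 1 h | exp(0.277) = 1.32 |
| 2 h | exp(0.554) = 1.74 |
| 3 h | exp(0.832) = 2.30 |

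At 3 h the ratio is exp(0.693) = 2.00 for a 3 h half-life and exp(1.040) = 2.83 for a 2 h half-life. If engagement depends on the concentration present at sampling, any concentration read off the plot for a given engagement is too high by the same factor.

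**Step 3: the formula as printed.** Section 9.1.1.1 prints an addition with a negative exponent: predicted trough = pre-dose value + exp(−ke × t). At 3 h and a 2.5 h half-life this adds exp(−0.832) = 0.44 units, and for any positive delay it adds less than 1. A pre-dose value of 50 becomes 50.4, where the multiplicative form gives 50 × 2.297 = 114.9. The printed form does not recover the SAP's example either: 50 + exp(−0.693) = 50.5, not 100. That is a separate error. Here it means that the fold-changes in Step 2 hold only if the multiplicative form is what gets programmed.

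**Step 4: with same-sample pairing.** If engagement is plotted against the observed concentration from its own sample, the ratio is 1.00 at every delay.

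**The case against.** The strongest reply is that no listed display shows the bias. The only concentration-engagement figures are 4.7 and 4.18. Both titles use pre-dose concentration, and the predicted trough is titled only against endoscopy remission and the efficacy endpoints. On this view the display list already makes the right split, and one line of text needs tidying.

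Much of this stands. A biased figure is not certain. But the display list does not override section 9.3 and Table 1, and it is not clean itself. The axis note to Figure 4.18 says trough. Neither 4.7 nor 4.18 says observed in its title, as Figures 4.4 to 4.6 do. The notes to Figures 4.4 and 4.5 also use trough for observed values, so the note to 4.18 can be read either way. The contradiction is clear for Figure 4.7 and rests on the title alone for Figure 4.18.

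A reader might infer more than the SAP supports:

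- **That the drug will look less potent.** This needs the multiplicative form and engagement that follows plasma without lag. The SAP gives no onset or offset kinetics for engagement, and no concentration for 50% engagement is to be estimated.
- **That Table 6.4 loses the trough correction.** The SAP does not say how predicted engagement is derived. Listing it apart from the observed engagement in Table 6.3 suggests that the two are kept distinct.
- **That Day 43 and Day 85 would be plotted on inconsistent axes.** The prediction is defined for Day 43 only, and section 9.3 does not say that the visits share a plot.
- **That tissue is affected too.** No predicted trough is defined for biopsy concentrations.
- **That this plot is the study's main evidence of target coverage.** Engagement is exploratory and is also summarised and modelled directly (Tables 6.3, 6.5 and 6.6).

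**Conclusion.** The point holds for Day 43 plasma. As written, section 9.3 and Table 1 pair engagement at the time of the clinic draw with a concentration for 7am, and this conflicts with Figure 4.7 and with the title of Figure 4.18.

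The size is conditional. With multiplicative back-extrapolation, the plotted concentration exceeds that in the sample by 1.32-fold at 1 h and 2.30-fold at 3 h (2.0 to 2.83 at 3 h across the stated half-life range). This becomes a bias of the same size in the exposure-engagement relation only if engagement tracks concurrent concentration. With lag it is smaller, though the values still refer to different times. Actual delays are not in the SAP. If the printed formula were programmed literally, the shift would be under 1 concentration unit and the contradiction in the text would remain.

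The consequence is confined to an exploratory graphical analysis; safety and efficacy results are untouched. It is worth correcting because two instructions for the same plot cannot both be followed.

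**What to change.** - In sections 2.1 (Table 1) and 9.3, limit the predicted trough to endoscopy remission and the efficacy endpoints, that is, Figures 4.8 to 4.17.
- In section 9.3, state that target engagement is plotted against the observed concentration from the same visit and sample type.
- Change the axis note of Figure 4.18 to observed pre-dose concentration.
- State how Table 6.4 is derived. If it uses a concentration-engagement relation, fit that relation on the observed same-sample pairs and only then apply it to the predicted troughs.

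The cost is SAP wording. No new data are needed: the observed concentrations and the Day 43 predicted troughs are both already summarised under Table 4.1, and the titles of Figures 4.7 and 4.18 already describe the right pairing.

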10. BIOMARKER ANALYSES

10.1. Biomarker/Target Engagement/Pathway Engagement/ Transcriptomics Analyses

10.1.1. Endpoint / Variables

Table 8 Overview of Planned Analyses

Endpoint	Absolute						Change from Baseline							
	Stats Analysis			Summary		Individual		Stats Analysis			Summary		Individual	
	T	F	L	T	F	F	L	T	F	L	T	F	F	L
Exploratory Biomarkers														
Inflammatory biomarkers in biopsy tissue ¹				Y		Y	Y	Y	Y	Y	Y			Y
Pathway and Target Engagement														
Pathway and target engagement in blood ²	Y	Y	Y	Y		Y ³	Y							
Pathway and target engagement in biopsy tissue ²	Y	Y	Y	Y		Y	Y							
Transcriptomics														
mRNA expression from blood ^{3 4}				Y		Y	Y	Y	Y	Y				
mRNA expression from biopsy tissue ^{3 4}				Y		Y	Y	Y	Y	Y				

NOTES:

- T = Table, F = Figure, L = Listing, Y = Yes display generated.
 - Stats Analysis = Represents TFL related to any formal statistical analyses (i.e. modelling) conducted.
 - Summary = Represents TF related to any summaries (i.e. descriptive statistics) of the observed raw data.
 - Individual = Represents FL related to any displays of individual participant observed raw data
- 1: Markers including but not limited to: IL-1, IL-6, IL-8, MMP-3, TNF α and IFN γ
- 2: TEAR1, phosphorylated or total RIP1, MLKL, and RIP3, cleaved and total caspase 3 and caspase 8 signatures in blood and biopsy tissue if sample quantity and data allow.
- 3: mRNA expression of inflammatory gene transcripts including but not limited to: IL-4, IL-10, IL-17, IL-21, IL-22, IL-23, TNF and IFN γ .
- 4: Data to be analysed by the GSK II Statistics and Programming Team Post-SAC.

Scatter plots of Target Engagement and blood/biopsy tissue biomarkers for Day 43 and Day 85 will also be produced.

If deemed appropriate, the relationship between Target Engagement and the blood/biopsy tissue biomarkers will be explored further using multivariate statistical analyses. The consistency in the changes over time between the endpoints will also be assessed. Any such analyses will be defined after unblinding of the data and thus deemed post-hoc.

10.1.2. Population of Interest

The pharmacodynamic/biomarker analyses will be based on the Safety population, unless otherwise specified.

10.1.3. Statistical Analyses / Methods

Details of the planned displays are provided in [Appendix 10: List of Data Displays](#) and will be based on GSK Data Standards and statistical principles.

Unless otherwise specified, endpoints / variables defined in Section 10.1.1 will be summarised using descriptive statistics, graphically presented (where appropriate) and listed.

Biomarker data will be summarised for Parts A and B combined by randomised treatment.

10.1.3.1. Statistical Methodology Specification

Exploratory Inflammatory Biomarkers
Endpoints

 Change from baseline on log transformed inflammatory biomarkers in biopsy tissue on Day 43 pre-dose and Day 85: $\text{Log}_e \text{ Change} = \text{Log}_e (\text{Visit}) - \text{Log}_e (\text{Baseline})$. 
Markers include but not limited to: IL-1, IL-6, IL-8, MMP-3, TNFα and IFNγ.

Model Specification

 Endpoints will be statistically analyzed using a mixed model repeated measures (MMRM) approach. Terms fitted in the MMRM model will include: 
 Fixed Category : Treatment, Day, Treatment*Day Fixed Continuous Covariates : Baseline Score, baseline*Day Repeated Effect : Day The Kenward and Roger method for approximating the denominator degrees of freedom and correcting for bias in the estimated variance-covariance of the fixed effects will be used. An unstructured covariance structure for the R matrix will be used by specifying 'type=UN' on the REPEATED line with a subject=SUBJID option.
Model Checking & Diagnostics

 For the MMRM, model assumptions will be applied, but appropriate adjustments may be applied based on the data. In the unlikely circumstance that there are convergence problems with the MMRM analysis, this will be explored. For example, the SCORING=4 option could be used in the MIXED statement, which makes SAS use Fisher scoring for the first 4 iterations. If the convergence problem cannot be resolved, the unstructured covariance matrix will be replaced by ANTE (1) covariance structure in combination with a

random participant effect.
 
 ○ If this model fails to converge, alternative correlation structures may be considered such as CS or AR (1). ○ Akaike's Information Criteria (AIC) will be used to assist with the selection of covariance structure. 
 ● Distributional assumptions underlying the model used for analysis will be examined by obtaining a normal probability plot of the residuals and a plot of the residuals versus the fitted values (i.e. checking the normality assumption and constant variance assumption of the model respectively) to gain confidence that the model assumptions are reasonable. ● If there are any departures from the distributional assumptions, alternative models will be explored using appropriate transformed data.

Presentation of results

 ● Adjusted geometric means, the mean difference between each dose (test) and the placebo (reference) at each timepoint and associated 95% confidence interval will be constructed using the residual variance. ● The treatment ratios and 95% CI will be calculated by back-transforming the difference between the least square means and associated 95% CI. ● Percentage change from baseline at each timepoint will be calculated from the adjusted geometric means using the formula $100\% \times (\exp(\text{adj mean}) - 1)$.

Pathway and Target Engagement

Endpoints

 ● $\text{Log Ratio} = \text{Log}(\text{free TEAR1}) - \text{log}(\text{total TEAR1})$.

Model Specification

 ● A mixed effect model will be fitted with randomised treatment, time (i.e. planned relative time) and randomised treatment * time as a fixed effect and participant as a random effect. Baseline log ratio will be fitted as a continuous covariate along with Baseline log ratio* time. ● The Kenward and Roger method for approximating the denominator degrees of freedom and correcting for bias in the estimated variance-covariance of the fixed effects will be used. ● An unstructured covariance structure for the R matrix will be used by specifying 'type=UN' on the REPEATED line with a subject=SUBJID option.

Model Checking


 ● For the MMRM, model assumptions will be applied, but appropriate adjustments may be applied based on the data. ● In the unlikely circumstance that there are convergence problems with the MMRM analysis, this will be explored. For example, the SCORING=4 option could be used in the MIXED statement, which makes SAS use Fisher scoring for the first 4 iterations. If the convergence problem cannot be resolved, the unstructured covariance matrix will be replaced by ANTE (1) covariance structure in combination with a random participant effect. ● If this model fails to converge, alternative correlation structures may be considered such as CSH or CS. ● Distributional assumptions underlying the model used for analysis will be examined by obtaining a normal probability plot of the residuals and a plot of the residuals versus the fitted values (i.e. checking the normality assumption and constant variance assumption of the model respectively) to gain confidence that the model assumptions are reasonable. ● If there are any departures from the distributional assumptions, alternative models will be explored using appropriate transformed data.

Pathway and Target Engagement
Presentation of Results

 Adjusted geometric means, the mean difference between each dose (test) and the placebo (reference) at each timepoint and associated 95% confidence interval will be constructed using the residual variance. The treatment ratios and 95% CI will be calculated by back-transforming the difference between the least square means and associated 95% CI. Percentage target engagement at each timepoint will be calculated from the adjusted geometric means using the formula: $100\% \times (\exp(\ln(v_2 / v_1) + 1))$ percentage target engagement = $(1 - \text{engagement ratio}) * 100$.

Transcriptomics – Fold Change Analysis

 The \log_2 normalised copy numbers (also referred to as $\log_2(\text{intensity})$) received from the normalised process will be listed and summarised appropriately by randomised treatment. As the data will be \log_2 transformed prior to the analysis, the randomised treatment effects will be expressed as ratios after back transformation to the original scale. These ratios can be converted from randomised treatment ratios to fold change values as follows: 
 If ratio ≥ 0 then fold change = ratio If ratio < 0 then fold change = $-1/\text{ratio}$
Endpoint(s)

 $\log_2(\text{intensity})$ mRNA expression of inflammatory gene transcripts
Model Specification

 Endpoints will be statistically analyzed using a linear repeated measure mixed effects model. Terms fitted in the linear repeated measures mixed effects model will include: 
 Fixed Category : Treatment, Visit, Treatment * Visit Random Effect : Participant
Model Checking & Diagnostics

 Model assumptions will be applied, but appropriate adjustments may be applied based on the data. In the unlikely circumstance that there are convergence problems with the analysis, this will be explored. If this model fails to converge, alternative correlation structures may be considered such as CSH or CS. Distributional assumptions underlying the model used for analysis will be examined by obtaining a normal probability plot of the residuals and a plot of the residuals versus the fitted values (i.e. checking the normality assumption and constant variance assumption of the model respectively) to gain confidence that the model assumptions are reasonable. If there are any departures from the distributional assumptions, alternative models will be explored using appropriate transformed data.
Presentation of Results

 For each probeset analysed adjusted means with corresponding 95% CI and fold changes with corresponding 95% CI's can be outputted. The fold change is derived from the ratio of the back-transformed estimate of the difference between adjusted means. Plots of LS means and 95% confidence intervals from the model will be generated for each treatment by time. Additionally, plots of differences and 95% confidence intervals for the comparison between the treatment groups will be generated. For each comparison subsets of probesets will be identified based on an appropriate fold-change, for example, fold changes >1.5 or <-1.5. The proportion of probesets with fold changes >1.5 or <-1.5 will

Transcriptomics – Fold Change Analysis

be summarised in a frequency table.

- Exploratory graphical reporting on the back-transformed scale can include:
 - \log_2 (intensity) plotted against time point separately for individual participants, grouped by randomised treatment group
 - Adjusted mean intensity and 95 CI% plotted by treatment group and time point.

Transcriptomics - MicroArray RNA Analysis

- MicroArray RNA will be extracted and hybridised using a balanced batch design by Epistem. An appropriate microarray platform will be determined at the time of hybridisation, to allow for improvements in technology. The quality of the data will be assessed and then normalised using appropriate methodologies and software.
- Microarray mRNA data will be normalised using gcRMA or RMA in Array Studio v5.0 or later. After normalisation, the data will be quality assessed and any samples deemed as QC fails will be excluded from any further analysis. This quality assessment will involve looking for outlying signals in both the normalised expression data and the MAS5 QC metrics generated from each sample. If any samples are excluded, the remaining data will be re-normalised. The output from the normalisation will be \log_2 transformed mRNA intensity data (measured in arbitrary units).
- Microarray data consists of expression values (\log_2 -transformed) derived from individual probesets designed against coding regions of individual genes. More than one probeset can exist per gene. This analysis will be conducted at the probeset level.
- To identify the most robustly expressed probesets, the data can be filtered to remove low intensity probesets, low quality and control probe sets prior to analysis. This could be done simply by excluding all probesets where all observations are <6 (on the \log_2 scale). Note it has been observed empirically that when you get below 100 (6.6 on the \log_2 scale) you are into the noise of the assay. Other more stringent methods of filtering the data could be used. In total, there are 53,617 probesets that could be analysed.
- To compare the expression value for each probeset, the following linear repeated measures mixed effects model will be fitted to each probeset that passes any pre-filtering, with \log_2 (intensity) as the response variable. Randomised Treatment by visit, randomised treatment and visit will be fitted as fixed effects and participant as a random effect. Example SAS code is given below:

```
proc mixed data=data;
ods output covparms=cov lsmeans=lse estimates=Compare;
class subjid treatment visit;
model lgintensity= treatment visit treatment*visit /ddfm=kr;
repeated visit / subject=subjid type=un;
lsmeans treatment*visit / diff cl alpha=0.05;
run;
```

- For each probeset analysed adjusted means with corresponding 95% CI and fold changes with corresponding 95% CI's can be outputted. The fold change is derived from the ratio of the back-transformed estimate of the difference between adjusted means.

Transcriptomics - MicroArray RNA Analysis

- Where appropriate, particularly with microarray data, multiple testing will be considered using the Benjamini-Hochberg correction (*Benjamini, Y; J Royal Stat Soc 1995;57:289-300*) to calculate FDR adjusted p-values. Proc Multtest incorporating the FDR adjusted p-value option in SAS is used to convert the raw p-values from the proc mixed code above into the FDR adjusted p-values based on the Benjamini-Hochberg correction. Example code to generate the FDR adjusted p-values is given below:

```
data pvalues (keep = probsid label probt rename=(probt=raw_p));
    set compare;
run;

proc multtest pdata=pvalues fdr out=FDRres noprint;
run;
```

- Where the FDRes dataset will include the following columns:

p-values		
Test	Raw	False Discovery Rate
1	0.2828	0.9243
2	0.9437	0.9437
3	0.0350	0.6305
etc.		

- Appropriate outputs will be created containing all the results for the relevant comparisons for all analysed probesets. A summary may be generated, including probeset ID, gene ID, time point, adjusted means with corresponding 95% CI for each randomised treatment group, Benjamini-Hochberg FDR adjusted p-value and fold changes corresponding 95% CI from each comparison. Note that probeset ID is required if there is more than one probeset per gene.
- For each comparison subsets of probesets will be identified based on an appropriate fold-change, for example, fold changes >1.5 or <-1.5. The proportion of probesets with fold changes >1.5 or <-1.5 will be summarised in a frequency table.
- The outputs should be reviewed by the study team and the pre-agreed subset of biologically relevant probesets will be reported within the CSR. If based on the fold-changes observed other probesets, which were not pre-specified in the RAP, are deemed relevant then these should be interpreted with caution.
- Exploratory graphical reporting on the back-transformed scale can include:
 - Log₂ (intensity) plotted against time point separately for individual participants, grouped by randomised treatment group
 - Adjusted mean intensity and 95 CI% plotted by randomised treatment group and time point.

Transcriptomics – Microarray Percentage Inhibition Analysis

- The \log_2 normalised data is back transformed and the percentage inhibition is derived on a participant level on the back transformed data for each probeset. The percentage inhibition will be determined for each probeset per participant, where it is defined as the reduction from baseline. For example:

Day X – baseline = -40% would be a 40% reduction (i.e. -40% change from baseline) which in turn is defined as a 40% inhibition. So, the percentage inhibition would be calculated as:

$$[(\text{Day } x - \text{Baseline}) / \text{Baseline}] * -100 = \% \text{ inhibition}$$

- A subset of probesets may be identified and individual participant mRNA intensities and percentage inhibitions may be listed, summarised and plotted appropriately for each selected probeset. The selected probesets will be statistically analysed appropriately, and the output from the mixed effects model summarised. The probeset, gene or gene description will be included in the outputs.
- To compare the percentage inhibition for each selected probeset, the following linear repeated measures mixed effects model will be fitted to each selected probeset, with percentage inhibition as the response variable. Randomised Treatment by visit, randomised treatment and visit will be fitted as fixed effects and participant as a random effect. Example SAS code is given below:

```
proc mixed data=data;
class subjid treatment visit;
model perinhibit= treatment visit treatment*visit /ddfm=kr;
repeated visit / subject=subjid type=un;
lsmeans treatment*visit / diff cl alpha=0.05;
run;
```

